#### **5.3.4 Analysis of Adverse and Serious adverse events**

Subject-level event rates will be calculated at various time points (e.g. exact days) based on all events reported by the site regardless of whether they are ultimately adjudicated. Frequency of site reported Serious adverse events and non-serious adverse events and also Frequency of site-reported Serious adverse events and Non-serious adverse events are associated with the implant procedure up to MRI Visit+1 Month are exhibited using counts and percent with total available subjects based on safety population. The events are summarized by MedDRA system organ class and MedDRA system preferred terms with events and rates.

For calculating events and rates, need to consider ‘Events numbers’ are total episodes of each type of event among all subjects. ‘Rate of Subjects with Event’ numbers are percent of subjects who experienced one or more episodes of the event. ‘Events’ numbers for “TOTAL” are the sum of the individual event category totals. ‘Rate of Subjects with Event’ numbers for “TOTAL” is the percent of subjects who experienced an adverse event.

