## **20.3. Risks Associated with Participation in the Clinical Study**

Subjects in the MR ICD Study will have the added risk of an MR scan. Potential adverse events associated with an MR scan are minimized by assuring that the subject meets the MRI Conditions of Use. MRI scanning of patients when the Conditions of Use are met could result in the following potential adverse events, as included in the *BSC MRI Tech Guide*:

- Arrhythmia induction
- Bradycardia
- Patient death
- Patient discomfort due to slight movement or heating of the device
- Side effects of pacing at a fixed high rate such as competition with intrinsic rhythms and arrhythmias. Competitive pacing may increase the rate of pacing induced

arrhythmia until the device is reprogrammed.

- Syncope
- Worsening heart failure

MRI scanning of patients when the Conditions of Use are NOT met could result in the following potential adverse events, as included in the *BSC MRI Technical Guide*:

- Arrhythmia induction
- Bradycardia
- Damage to the pulse generator and/or leads
- Erratic pulse generator behavior
- Inappropriate pacing, inhibition of pacing, failure to pace
- Increased rate of lead dislodgement (within six weeks of implant or revision of system)
- Irregular or intermittent capture or pacing
- Loss of defibrillation therapy
- Pacing threshold changes
- Patient death
- Patient discomfort due to movement or heating of the device
- Physical movement of pulse generator and/or leads
- Sensing changes
- Syncope
- Worsening heart failure

\*\*Note: It is important to note that the risks listed in this section may lead to the subject requiring a partial or full pacing system replacement.

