## **21. Safety Reporting**

### **21.1. Reportable Events by investigational site to Boston Scientific**

It is the responsibility of the investigator to assess and report to BSC any event which occurs in any of following categories:

- All Serious Adverse Events
- All Investigational Device Deficiencies
- Unanticipated Adverse Device Effects/Unanticipated Serious Adverse Device Effects
- New findings/updates in relation to already reported events

When possible, the medical diagnosis should be reported as the Event Term instead of individual symptoms.

If it is unclear whether or not an event fits one of the above categories, or if the event cannot be isolated from the device or procedure, it should be submitted as an adverse event and/or device deficiency.

Any AE event required by the protocol, experienced by the study subject after informed consent and once considered enrolled in the study (as defined in study subject classification section), whether during or subsequent to the procedure, must be recorded in the eCRF.

Underlying diseases are not reported as AEs unless there is an increase in severity of frequency during the course of the investigation. Death should not be recorded as an AE, but should only be reflected as an outcome of ONE (1) specific SAE (see Table 21-1 for AE definitions).

Refer to Section 20 for the known risks associated with the study device(s).

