### **21.3. Relationship to Study Devices**

The Investigator must assess the relationship of the AE to the study device or procedure. See criteria in Table 21-2:

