**Table 21-3 Investigator Reporting Requirements**

Event Classification	Communication Method	Communication Timeline
Unanticipated Adverse Device Effect / Unanticipated Serious Adverse Device Effect	Complete AE eCRF page with all available new and updated information.	
 
• Within 24 hours of first becoming aware of the event
 
• Reporting required through the end of the study
 

Serious Adverse Event	Complete AE eCRF page with all available new and updated information.	
 
• Within 24 hours of first becoming aware of the event
 
• Reporting required through the end of the study
 

	Provide all relevant source	
 
• When documentation is
 

Event Classification	Communication Method	Communication Timeline
	documentation of the reported event	available
Serious Adverse Device Effects	Complete AE eCRF page with all available new and updated information.	
 
• Within 24 hours of first becoming aware of the event
 
• Reporting required through the end of the study
 

	Provide all relevant source documentation of the reported event	
 
• When documentation is available
 

Device Deficiencies (including but not limited to failures, malfunctions, and product nonconformities)  Note: Any Investigational Device Deficiency that might have led to a serious adverse event if a) suitable action had not been taken or b) intervention had not been made or c) if circumstances had been less fortunate is considered a reportable event.	Complete AE eCRF page with all available new and updated information.	
 
• Within 1 business day of first becoming aware of the event
 
• Reporting required through the end of the study
 

Adverse Event including Adverse Device Effects	Complete AE eCRF page, which contains such information as date of AE, treatment of AE resolution, assessment of seriousness and relationship to the device.	
 
• Within 10 business days after becoming aware of the information
 
• Reporting required through the end of the study
 

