### 5.1.2 Primary safety endpoint analysis:

The primary safety endpoint of the MR ICD study will be assessed for all subjects who undergo any portion of the study-required MR scan sequences. Safety will be confirmed by evaluating the MR scan related ImageReady System complication-free rate (CFR) between the MR Scan and the MRI Visit + 1 Month. This endpoint is analyzed based on Implant population. Counts and percentages presenting 95% Clopper-Pearson confidence interval with two-sided exact binomial confidence bound at 95%.

Complications that are determined to be associated with the MR scan will be considered MR scan-related complications and count against this endpoint. Complication is defined as serious adverse event or permanent loss of device functions (pacing/defibrillation).

All the primary efficacy endpoint and safety endpoint been summarized presenting 95% Clopper-Pearson confidence interval with two-sided exact binomial confidence made for both Intent and Implant study populations. If subject’s status been categorized to either Attempt or Partial Implant, then the results been presented for both these populations as well.

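### SAP 5.3.4 singles out adverse events tied to the implant procedure and plans no display by onset relative to the MR scan or by relation to it, although the scan is the exposure under study

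*Combined protocol and SAP*

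**What the plan says.** Protocol 20.3 names the exposure that the study adds to ordinary device care: "Subjects in the MR ICD Study will have the added risk of an MR scan". The scan takes place 6 to 9 weeks after implant (protocol 12.7).

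SAP 5.3.4 plans the adverse event output. It starts with rates whose timing is left open: "Subject-level event rates will be calculated at various time points (e.g. exact days". It then plans two displays by MedDRA class and term. The first is "Frequency of site reported Serious adverse events and non-serious adverse events". The second covers events that "are associated with the implant procedure up to MRI Visit+1 Month are exhibited using counts and percent". The scan is mentioned only through the visit name that closes the second window.

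Scan-related events have one dedicated analysis, the primary safety endpoint. SAP 5.1.2 states: "Complications that are determined to be associated with the MR scan will be considered MR scan-related complications and count against this endpoint". A complication there means an SAE or lasting loss of pacing or defibrillation.

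On causality, protocol 21.3 says: "The Investigator must assess the relationship of the AE to the study device or procedure". On reporting, the list in protocol 21.1 has "All Serious Adverse Events", device deficiencies, unanticipated device effects and updates, with no line for non-serious AEs. Table 21-3 has a row for "Adverse Event including Adverse Device Effects", due within 10 business days and through the end of the study.

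**The concern.** A reader of the safety report will want to know what happened to subjects at and after the scan. The planned AE output is organised around the implant. Implant complications cluster naturally in the first weeks, before any subject is scanned, and the overall display would merge them with events that follow the scan.

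Protocol 20.3 lists effects that may occur even when the Conditions of Use are met, including discomfort from movement or heating of the device, bradycardia and syncope. Non-serious instances fall outside the primary endpoint by definition, so the AE tables are where they would be seen. If those tables do not separate the periods, a handful of such events among about 20 subjects could not be told apart from implant-related ones.

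There is also a mismatch in the reporting rules. Protocol 21.1 and Table 21-3 differ on whether non-serious AEs are reportable, so completeness could vary with the section a site follows.

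**Working it through.** The plan states no figure on this point, so there is none to reproduce. The check compares the texts and adds window arithmetic.

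**1. What each planned output can show about events at or after the scan**

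| Output | Scan-specific? | What it leaves out |
|---|---|---|
| Primary safety endpoint (protocol 13.1.1, SAP 5.1.2) | Yes, scan to MRI + 1 Month | Non-serious AEs without lasting loss of function; SAEs not reported or adjudicated as scan-related |
| Post-scan VT/VF (protocol 13.2.3, SAP 3.3) | Yes | Anything other than VT/VF episodes from the Arrhythmia Logbook |
| All site-reported AEs and SAEs (SAP 5.3.4) | No stated window or anchor | Any split at the scan |
| Implant-procedure subset (SAP 5.3.4) | No | Events attributed to the scan, or a split at the scan, depending on how the sentence is read |
| Death listing (SAP 5.3.1) | No; days counted from implant | Time from scan |

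The sentence behind the implant subset is grammatically broken and has two readings. If it means events attributed to the implant procedure, it selects a different exposure from the scan. If it means all events from implant to MRI + 1 Month, it pools the periods before and after the scan. Neither reading gives a scan-emergent table.

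**2. Route into the primary endpoint**

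Under protocol 13.1.1 and 23.2, the complications sent for adjudication are those the site has reported as related to the scan and the system. A post-scan SAE that the site does not attribute to the scan therefore does not enter the endpoint. It would appear only in the pooled table.

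**3. Time before and after the scan**

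Inputs: implant to scan 42 to 63 days (protocol 12.7); scan to MRI + 1 Month 30 ± 7, that is 23 to 37 days (protocol 12.8). Assumption: no surgical revision, which would lengthen the interval from implant.

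- Shortest and longest total: 42 + 23 = 65 days; 63 + 37 = 100 days.
- Pre-scan share = pre / (pre + post). Smallest: 42 / (42 + 37) = 42/79 = 53%. Largest: 63 / (63 + 23) = 63/86 = 73%.
- Post-scan share: 37/79 = 47% down to 23/86 = 27%.

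These are shares of calendar time. They show that the window is not scan-specific and do not estimate how many events would be mixed.

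**4. Reporting rules side by side**

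- Protocol 21.1: no line for non-serious AEs. It then asks for eCRF entry of whatever AEs the protocol requires, which does not settle the question.
- Table 21-3: AEs within 10 business days, with no limit to related events.
- Table 12-1: AE collection at every visit.
- SAP 5.3.4: non-serious AEs are tabulated.

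Three of the four places expect non-serious AEs, and the 21.1 list is the odd one out.

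**5. Details that affect a split by period**

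SAP 7.3 replaces a wholly missing onset date with the procedure date without saying which procedure. If that is the implant, a post-scan event would move to before the scan. SAP 5.3.4 also refers to a safety population, which SAP 4.1 does not define.

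**The case against.** The strongest reply is that scan safety already has its own analysis. Independently adjudicated scan-related complications are the primary endpoint with an exact 95% interval, post-scan VT/VF is summarised and the logbook listed, rhythm is monitored during the scan, and protocol 21.7 sends deaths to the events committee. This stands. A reader might infer that scan-emergent events are never shown separately, and the documents do not support that. What remains is the two groups outside those displays. The VT/VF summary also does not reach into the scan itself, because tachycardia detection is suspended in MRI Protection Mode (protocol 5.1).

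A reader might also infer that the 21.1 list causes the missing table, or that non-serious AEs go uncollected. Neither follows. Table 21-3, Table 12-1 and SAP 5.3.4 all provide for them, and the missing split comes from SAP 5.3.4 alone. The 21.1 mismatch is a separate drafting point.

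On 21.3, the scan can fairly be read as a study procedure, and protocol 13.1.1 presupposes that sites report relation to it. The eCRF is not among the documents, so it cannot be said that a scan-relationship field is missing. What can be said is that 21.3 does not name the scan.

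Finally, the 53% to 73% should not be read as the share of events that precede the scan. The window is attached, on the plainer reading, to the implant subset, where pre-scan time is expected, and the overall display has no stated window.

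**Conclusion.** The point holds in a limited form. SAP 5.3.4 specifies no display of AEs by onset relative to the scan or by relation to it, and the one subset it singles out concerns the implant. Non-serious scan-emergent AEs, and post-scan SAEs not adjudicated as scan-related, would be pooled with pre-scan events. The number of events affected cannot be derived from the documents.

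This is a gap in descriptive reporting. The primary endpoint is unaffected, and there is no hypothesis test to distort. It is still worth closing, because in a study of about 20 subjects the description of what followed the scan is much of the safety evidence. The conclusion rests on the SAP text as the full specification of AE output; the undefined time points could be anchored at the scan in practice, but the plan does not say so. The disagreement between protocol 21.1 and Table 21-3 is real, separate and smaller.

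**What to change.** - **SAP 5.3.4:** tabulate SAEs and non-serious AEs by onset before the scan, from the scan to MRI + 1 Month, and from then to 1 year, and by reported relation to the MR scan. Name the population. In SAP 7.3, say which procedure date replaces a missing onset date, so that events are not moved across the scan by default.
- **Protocol 21.3:** state that procedure includes the MR scan and that relation to the scan is assessed separately, as 13.1.1 already presupposes. Check the eCRF for a matching item and add one only if it is absent.
- **Protocol 21.1:** reconcile the list with Table 21-3 without a relatedness restriction. Adding only related non-serious AEs would leave the two in disagreement, since the Table 21-3 row has no such limit.

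The split by period needs no new data: Table 21-3 puts the AE date on the eCRF and protocol 12.7.3.3 records scan times. The cost is one extra set of tables, a few lines of text and slightly more AE entry for about 20 subjects.

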### 5.3.5 *Protocol Deviations*

A summary table for Deviations from Investigational Protocol collated during procedure and post procedure for all the planned events as specified in protocol.

- Enrollment
- Implant
- Pre-Discharge
- Partial Implant / Attempt + 1 Month
- Medically Necessary Scan(MNS)
- MRI Visit
- MRI Visit + 1 Month
- MRI Visit + 3 Month
- MRI Visit + 6 Month
- MRI Visit + 9 Month
- 1 Year Follow-up Visit
- Additional Visit
- Adverse Events
- Cardiovascular Medications
- Device Deficiency
- End of Study

A summary table by protocol deviation are summarized with counts and percent and another summary table presented based on deviations reasons

### 5.3.6 *Device Deficiencies*

A table exhibited based on device deficiencies with out of service reasons been presented with count and percent for the available parameters with a supported listing. Also, a listing based on Device deficiency identifier with description and connected to SAE with occurrence instance been listed for Implant population.

#### 5.4 Changes to Planned Analyses

Any changes to the planned statistical analyses made prior to performing the analyses will be documented in an amended Statistical Analysis Plan approved prior to performing the analyses. Changes from the planned statistical methods after performing the analyses will be documented in the clinical study report along with a reason for the deviation.

### 6. VALIDATION

All clinical data reports generated per this plan will be validated per [90702587](#), Global WI: Clinical Data Reporting Validation. The validation level R1 chosen for all primary, secondary, safety and other additional endpoints.

The validation program includes checking logs and generating compare reports in comparing with main programming datasets.

### 7. PROGRAMMING CONSIDERATIONS

All statistical programming tasks will be performed by IQVIA™ independently.

#### 7.1 Statistical Software

All statistical analyses will be done using The SAS System Version 9.2 software or above (Copyright © 2000 SAS Institute Inc., [name]. All rights reserved.).

#### 7.2 Format of Output

Results of analysis will be output programmatically to Microsoft Office® Word documents from SAS with no manual intervention. All output for the final statistical report will be in the form of a Word document containing tables, figures, graphs, and listings, as appropriate.

#### 7.3 Methods for Handling Missing Data

No imputation method will be performed for the missing data handling.

Missed or late visits will be recorded as Protocol Deviations.

When calculating rates of treatment-emergent adverse events, missing and partial dates will be handled as shown in the table below.

Partial Date	Action Taken
Entire adverse event onset date is missing	The procedure date will be used for the onset date.

Partial Date	Action Taken
The month and the day of the month are missing but the year is available	January 1 st will be used for the month and day of the onset date. However, if the imputed date falls before the procedure date, then the procedure date will be used for the onset date.
Day is missing, but the month and year are available	The 1 st will be used as the day of the onset date. However, if the imputed date falls before the procedure date, then the procedure date will be used for the onset date.

#### 7.4 Rules and Definitions

For baseline categorical variables, missing values will not be counted in rate denominators. Number of patients completing the visit will be considered in denominators.

#### 7.5 SAS code for Clopper-Pearson

The confidence intervals for Clopper-Pearson and binomial proportion of CI are produced using PROC FREQ procedure. Below is a glimpse of sample code to extract the required values. For example, for the primary endpoint hypotheses for deriving Clopper-Pearson confidence limits, using the below dummy frequency table, coded as below:

```

data main;
  input code $4. count;
  datelines;
yes 56
no 4
;
run;
proc freq data=main order=freq;
  tables code / binomial (exact ) alpha=.05;
  tables code / binomial (cl=Wald ) alpha=.05;
  weight Count;
run;

```

The SAS code is presented for the binomial proportion for 95% Clopper-Pearson confidence intervals is specified. The use of ORDER=FREQ, in the SAS program, keep the highest frequency of success/failure as base and option binomial (EXACT) with alpha=0.05 will generate 95% Clopper-Pearson Confidence limits. We also get Wald's (Asymptotic) 95 % Confidence limits that need to present in the exhibit.

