### 3.5 Sample Size

The MR ICD study is a small sample size study without any formal hypothesis testing. Twenty subjects (10 with ICD and 10 with CRT-D) will be enrolled. It is assumed that the attrition should not be more than 2 cases in each group, so that at least 8 ICD subjects (at least 1 single chamber and 1 dual chamber ICD) and 8 CRT-D subjects shall undergo required MR scan and complete all the sequences. Sample size might be expanded to meet this assumption.

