### 5.1.1 Primary efficacy endpoint analysis:

The primary effectiveness endpoints are defined as ‘a success based on the specified criteria conditions earlier’, otherwise it’s a failure (event) .

All the 5- primary endpoints are based on Implant population,

- Pre-MR Scan vs. 1 Month Post-MR Scan RV shocking impedance
- Pre-MR Scan vs. 1 Month Post-MR Scan RV Pacing Threshold at 0.5 ms
- Pre-MR scan vs. 1 Month Post-MR Scan RV Sensed Amplitude
- Pre-MR Scan- vs. 1 Month Post-MR Scan LV Pacing Threshold at 0.5 ms
- Pre-MR scan vs. 1 Month Post-MR Scan LV Sensed Amplitude

are summarized descriptively with counts and percentages presenting 95% Clopper-Pearson confidence interval with two-sided exact binomial confidence bound at 95% will be presented to anticipate that the endpoint success is more than the lower bound of the confidence limits.

The time window for MRI + 1 Month visit is  $30\pm 7$  days post MR scan, so it will capture events within at least 23 days post scan for all the endpoints and Missing data will not be considered in the denominator part while deriving confidence limits and performance goals.

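### SAP 7.5 requires Wald 95% limits beside the exact ones, but with 8 to 20 subjects and high success rates they collapse to 100%-100% or badly overstate precision

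*Combined protocol and SAP*

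**What the plan says.** For the five effectiveness endpoints, SAP 5.1.1 names one interval: "95% Clopper-Pearson confidence interval with two-sided exact binomial confidence bound at 95% will be presented". SAP 5.1.2 does the same for the safety endpoint: "Counts and percentages presenting 95% Clopper-Pearson confidence interval with two-sided exact binomial confidence bound at 95". Neither section mentions an asymptotic interval.

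SAP 7.5, which gives sample SAS code, adds a second TABLES statement, "tables code / binomial (cl=Wald ) alpha=.05", and closes with an output requirement for the Wald limits: "Asymptotic) 95 % Confidence limits that need to present in the exhibit". It gives no reason, does not say which interval governs, and says nothing about an endpoint with no failures. No continuity correction is requested. The same section explains the ordering option: "The use of ORDER=FREQ, in the SAS program, keep the highest frequency of success/failure as base".

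On size, SAP 3.5 says "Twenty subjects (10 with ICD and 10 with CRT-D) will be enrolled" and allows for at most two losses per group.

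**The concern.** The Wald interval relies on the observed proportion being roughly normal with a well-estimated variance. Neither holds with 8 to 20 subjects and success near 100%. With no failures the estimated variance is zero and the interval shrinks to a point, which reads as certainty. With one or two failures it is centred too close to 100% and runs past it.

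The limits will be read against benchmarks. Protocol 13.1 quotes the global study's performance goals: 90% for safety, 87% for the two pacing thresholds and 85% for the two sensed amplitudes. SAP 3.4 treats the individual performance goal as a kind of hypothesis for judging each endpoint, and SAP 5.1.1 mentions confidence limits and performance goals together. A table with two intervals, both labelled 95% and pointing in opposite directions relative to those goals, invites quotation of the flattering one. SAP 1.2 says the study is to support regulatory approval.

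A smaller point concerns the code. Because `ORDER=FREQ` takes the more frequent outcome as the base, the data decide which proportion is reported. An endpoint on which most subjects failed would print the interval for the failure rate.

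**Working it through.** **Denominators.** SAP 3.5 gives 10 per group less at most 2, so 10 − 2 = 8 per group and 20 − 4 = 16 in total, which reproduces its minimum of 8 per group. Whole-sample endpoints therefore have 16 to 20 subjects, and the LV endpoints (CRT-D only) have 8 to 10. Endpoint 5 can be smaller, because SAP 4.1 removes subjects with a pre-scan LV amplitude below 5 mV. SAP 5.1.1 also takes missing data out of the denominator.

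**Formulas.** With x successes in n and p̂ = x/n:

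- Wald: p̂ ± 1.96 √(p̂(1 − p̂)/n).
- Clopper-Pearson: beta quantiles. With x = n the lower limit is 0.025^(1/n) and the upper limit is 100%.
- Coverage at true rate p: the sum of binomial probabilities P(X = x) over every x whose interval contains p.

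**Limits for 0, 1 and 2 failures (%).**

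| Successes | Wald | Exact |
|---|---|---|
| 8/8 | 100 to 100 | 63.1 to 100 |
| 10/10 | 100 to 100 | 69.2 to 100 |
| 16/16 | 100 to 100 | 79.4 to 100 |
| 20/20 | 100 to 100 | 83.2 to 100 |
| 7/8 | 64.6 to 110.4 | 47.3 to 99.7 |
| 9/10 | 71.4 to 108.6 | 55.5 to 99.7 |
| 15/16 | 81.9 to 105.6 | 69.8 to 99.8 |
| 19/20 | 85.4 to 104.6 | 75.1 to 99.9 |
| 18/20 | 76.9 to 103.1 | 68.3 to 98.8 |

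For 19/20 the half-width is 1.96 √(0.95 × 0.05/20) = 0.0955, so the Wald limits are 0.95 ± 0.0955. In the rows with one or two failures the Wald lower limit exceeds the exact one by between 8.6 points (18/20) and 17.3 points (7/8).

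**Against the goals.** With at most 20 subjects the exact lower limit cannot exceed 83.2%, so it never reaches 85%, 87% or 90%. With no failures the Wald lower limit is 100% and clears all three. At 19/20 it clears 85% but not 87% or 90%.

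**Coverage of the nominal 95% interval (%).** The true rate is assumed, so a range is shown.

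| n | Wald, true 90% | Wald, true 95% | Wald, true 98% | Exact, true 90% | Exact, true 95% |
|---|---|---|---|---|---|
| 8 | 56.5 | 33.6 | 14.9 | 99.5 | 99.4 |
| 10 | 65.0 | 40.0 | 18.3 | 98.7 | 98.9 |
| 16 | 81.1 | 55.9 | 27.6 | 98.3 | 99.3 |
| 20 | 87.6 | 63.9 | 33.2 | 98.9 | 98.4 |

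Worked case, n = 8 and p = 0.95: the Wald interval contains 0.95 only when x = 5, 6 or 7. Their probabilities are 0.0054 + 0.0515 + 0.2793 = 0.336. The outcome x = 8, with probability 0.95^8 = 0.663, gives the zero-width interval and always misses. Truncating the limits to 0-100% leaves coverage unchanged. At n = 6, possible for endpoint 5, coverage at a true rate of 95% is 26.3%.

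**How likely the collapse is.** At a true rate of 95% the chance of no failures is 66.3% (n = 8), 59.9% (n = 10) and 35.8% (n = 20).

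**The SAP's own example.** The dummy table has 56 successes in 60, giving Wald 87.0% to 99.6% and exact 83.8% to 98.2%. The lower limits differ by only 3.2 points. That n is three times the planned trial and at least six times the planned LV denominators, so the example does not show the problem.

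**The case against.** The strongest counter-argument is that the Wald limits decide nothing. The analysis sections name only Clopper-Pearson, acceptance is a count of at most two failures, there is no hypothesis test, and no section compares a Wald limit with a goal. The Wald text appears once, under a heading about Clopper-Pearson, next to a dummy table, and the exact interval would be printed alongside. It is true that no endpoint verdict depends on it, which limits the weight of the point. It does not make the text harmless. The closing sentence of 7.5 is an output requirement and not merely sample code, and intervals are the plan's only statement of precision for the primary endpoints.

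Other reservations also stand:

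- The 95% true rate is not a document figure, and 33.6% to 63.9% is a range across n = 8 to 20, not at one n. At the printed goals the whole-sample endpoints do better: for n = 16, 18 and 20, coverage is 81% to 88% at a true rate of 90%, 88% to 93% at 87% and 82% to 93% at 85%. Above 95% it is worse.
- The one-failure example against the 85% goal needs exactly 20 analysable subjects. With one failure the Wald lower limit is already 84.7% at n = 19 and 81.9% at n = 16. In practice it can arise only for RV sensed amplitude (endpoint 3), with no attrition or exclusions.
- The `ORDER=FREQ` fault needs a majority of failures, about a 0.0015% chance at n = 8 and a true rate of 95%. Such an endpoint would also breach the two-failure rule at n = 8 or more.
- A dummy table need not match the trial's size.

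The last two are therefore minor. The zero-width interval and the limits above 100% depend on none of these assumptions.

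**Conclusion.** The concern holds. SAP 7.5 requires an interval that 5.1.1 and 5.1.2 do not mention and that is invalid for these denominators. Whatever the true rate, it has zero width when there are no failures, and it passes 100% with one or two failures at the planned sizes checked. At assumed true rates of 90% and 95% its coverage ranges from 33.6% to 87.6% for n = 8 to 20, against at least 98% for the exact interval. The fault concerns presentation and interpretation and leaves the failure-count rule untouched. It should be corrected before the primary tables are produced, because the limits invite comparison with goals that the exact interval cannot reach at this size. The ordering option is a secondary coding point.

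**What to change.** In SAP 7.5, delete the Wald TABLES statement and the sentence requiring its limits in the exhibit. State once that Clopper-Pearson is the reported interval for all six primary endpoints. If a second interval is wanted, use Wilson: 67.6% to 100% for 8/8 and 83.9% to 100% for 20/20, with coverage of 91% to 96% at a true rate of 95% over these sizes. Replace `ORDER=FREQ` with an explicit success level in the BINOMIAL option, so that the printed proportion is always the success rate.

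The cost is two lines of SAP text and code. No new data are needed and the acceptance rule is unaffected. What is lost is an asymptotic interval that adds no valid information; what remains is wider, which is the correct picture of a study this small. If the sponsor wants the Wald limits kept, the minimum is a sentence making Clopper-Pearson the governing interval, but that would still print 100% to 100% when no failures occur.
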